2. STUDY PROCEDURES

a. Procedures

Participants will be recruited through flyers, online postings, and other postings at various clinics in the Bay Area. To determine eligibility, during screening participants will be asked their age, gender.

On the flyers and other recruitment materials, participants will be directed to a short survey on a secure platform that only asks for contact information to show interest in the study. The study team will use the contact information provided to set-up a phone screen for interested individuals. If the participant shows interest through one of the Honest Broker methods (such as MyChart) or through ResearchMatch.org which shares the contact information with the research team, then a member of the research team will reach out to the individual using the contact information provided to thank them for their interest and schedule a phone screen. See section 13 for the phone screen.

After the participant completes the phone screen, a member of the study team will contact them to confirm eligibility. Consent (for ages 18- 65) will be secured prior to enrollment.

Baseline Assessment:

After eligibility is confirmed but before groups begin, the participant will come in for their baseline assessment. At baseline, participants will complete the Paffenbarger Activity Questionnaire to assess physical activity, the Beck Depression Inventory, and the Eating Disorder Diagnostic Scale. We will also have participants get an HbA1c test and fasting glucose test through the Stanford CTRU. Finally, participants will complete a Bod Pod Assessment, measuring Body Fat. Prior to the start of groups, participants will complete the Automated Self-Administered 24-hr Dietary Recall (ASA-24) to assess dietary intake on 2 weekdays and 1 weekend.

Prevention program:

After baseline assessments are completed, participants will be randomized to either the Project Health groups or the educational control.

Randomization:

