If participants are randomized to Project Health, they will meet in groups of 6 individuals led by clinician. Groups will meet once a week in-person for an hour, for six weeks. Each week involves homework that participants are asked to complete before the next session. If participants are assigned to the Education intervention, they will be asked to watch one-hour of videos including information about T2D each week for six weeks.

Post-Test:

After the six weeks of either Project Health or the educational control, participants will be asked to complete the same assessments that they did at baseline, but not the blood tests.

3-Month Follow-up:

At 3-month follow-up, participants will again complete the assessments. After the 3-month follow-up, participants have completed all study responsibilities.

1-Year Follow-Up:

We propose to collect A1c data over 1 year follow up

First we will check to see in Epic if the participant is a Stanford patient.

If they haven't had a recent test or not in Stanford system we will ask if they would be willing to send any recent A1c blood test results.

If no to both, the participant will be offered to have an HbA1c kit sent to them to do a finger prick at home. The participant will send the kit to the research lab in Minnesota to be processed. Kits come with already pre-paid shipping labels that are addressed only to the Minnesota lab, no return address or any PHI from the participant is included. The participant will be offered a \$10 Amazon gift card for completing and shipping the HbA1c kit.

b. Procedure Risks

These research procedures provide minimal risk to subjects. We are using current and empirically evaluated measures and research staff available who have been fully trained both in administrating physiological interviews. Project Health has also been tested in

multiple trials and has produced only positive effects, there has been no history of symptoms worsening as a result of participating in the program.

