Evaluating a Type 2 Diabetes Prevention Program

NCT: 5822648

04/16/2023

**Analyses.** For the continuous response variables in Aims 1 and 2 we will fit linear mixed effects models (LME) or generalized additive models (GAM) if change across the study is nonlinear. All models will include an interaction of time since the start of the study (in months) and condition (as well as all lower-order main effects). For both LMEs and GAMs, we will control for the lack of independence between the observations within a participant by including random intercepts and random slopes (if necessary) for the participants in our models and for participants nested within groups.

To detect for differences in the onset of T2D (Aim 1) between the intervention and control condition, we will fit a Cox proportional hazard model using the survival package (Therneau, 2022) in R. The proportional hazard assumption will be assessed and in the event of violations of this assumption, stratified proportional hazard models will be fit.

For the mediation analysis for Aim 2, the mediation package (Tingley et al., 2014) in R will be used to employ the causal mediation approach described in Imai et al. (2010). This is a more general and flexible causal mediation framework than the traditional structural equation modeling approach to mediation. Specifically, this approach enables (1) definitions of causal mediation effects that are independent of a particular statistical model, (2) specification of the identifiability assumption, and (3) a framework that can be applied to a myriad of models (most importantly for this study, LMEs, GAMs, and survival models). In addition, sensitivity analyses can be conducted to explore the sequential ignorability assumption. Using this framework involves modeling the onset of T2D via a parametric survival regression model that includes condition and the proposed mediator (percent body fat). This model's output is then combined with the mediator model's output, the percent body fat model from Aim 1, and used to calculate the average causal mediation effect (ACME), the proportion of the total effect that is mediated as well as other mediation statistics, which can then be tested using either quasi-Bayesian Monte Carlo or the non-parametric bootstrap.

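### The SAP names no baseline covariate in the mediation models, so the effect attributed to body fat can be biased away from zero

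*SAP*

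**What the plan says.** The mediation paragraph of the SAP (Analyses) describes the T2D outcome model as "a parametric survival regression model that includes condition and the proposed mediator (percent body fat". Its output is combined with "the percent body fat model from Aim 1". The fixed terms of that second model come from the general rule at the start of the section: "All models will include an interaction of time since the start of the study (in months) and condition", plus the main effects, with participant random effects. No baseline body fat, HbA1c, fasting glucose or other pre-treatment variable is listed for either model.

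On the identifying assumption, the SAP says that "sensitivity analyses can be conducted to explore the sequential ignorability assumption". It gives no adjustment set. The ACME is to be tested by "quasi-Bayesian Monte Carlo or the non-parametric bootstrap", with no choice between them. The SAP does not say at which visit body fat enters, or whether as level, change or a model-derived slope.

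The candidate covariates are collected. Protocol section 2a says of baseline that "participants will complete a Bod Pod Assessment, measuring Body Fat" and "We will also have participants get an HbA1c test and fasting glucose test". At post-test "participants will be asked to complete the same assessments that they did at baseline", except that section 2a leaves out the blood tests; section 8m lists HbA1c at post-test.

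**The concern.** Randomisation makes the effects of condition on body fat and on onset comparisons between like groups. It does nothing for the association between body fat and onset, because nobody is randomised to a body-fat level. Sequential ignorability has to hold given the pre-treatment covariates in the models, and here none is named.

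A participant's body fat a few weeks after baseline is mostly their baseline body fat. If fatter participants already carry a higher T2D risk, the mediator coefficient picks up that standing difference between people. Multiplying it by the programme's effect on fat then yields a mediated effect that fat loss did not cause, and the direct effect moves the opposite way. Baseline glycaemia can act in the same way if it is correlated with fat; the three alternative prediabetes criteria in Protocol section 8h show that it varies between participants. The random intercept in the Aim 1 model absorbs between-person differences in the mediator model only; the outcome model as described has no counterpart.

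The timing gap adds to this. Under section 2a, fat and blood are measured together again at 3 months, so without a stated mediator visit a fat value could be treated as the cause of an onset detected at the same visit.

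**Working it through.** The documents give no event rate, effect size or ACME, and state the sample size of 62 (Protocol section 8a) without derivation, so there is no planned figure to reproduce. The check sets the true effect of fat change to zero and asks what the listed terms return.

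**Assumed inputs, none from the documents.** Baseline body-fat SD 7 points; SD of change 2 points; hazard ratio 1.6 per SD of baseline fat; programme effect on fat *a* = 1 or 2 points. Follow-up fat = baseline + change, and the hazard depends on baseline only.

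1. Share of follow-up variance that is baseline: 7² / (7² + 2²) = 49/53 = 92%.
2. False slope with condition and follow-up fat in the model: [ln(1.6)/7] × 49/53 = 0.0671 × 0.925 = 0.062 per point (truth 0).
3. False mediated hazard ratio, exp(−0.062*a*): 0.94 for 1 point, 0.88 for 2 points.
4. A Weibull regression on 150,000 simulated people also gave 0.062, with a false opposite direct effect (log hazard ratio +0.05 and +0.12). Adding baseline fat gave slopes of 0.006 and −0.001, and mediated hazard ratios of 0.99 and 1.00.
5. Weaker association, hazard ratio 1.2 per SD: [ln(1.2)/7] × 49/53 = 0.024 per point, so 0.98 for 1 point and 0.95 for 2 points.

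**Absolute-risk scale.** A second large-sample simulation used baseline SD 7, change SD 2.5, *a* = 2 and a 10% 12-month onset rate (all assumed), again with zero true indirect effect. ACME is in percentage points (pp):

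| What carries the risk | SAP terms | Baseline fat and HbA1c added |
|---|---|---|
| Baseline fat, HR 1.5 per SD | −0.96 | 0.00 |
| Baseline fat, HR 1.2 per SD | −0.44 | +0.03 |
| HbA1c, HR 2 per SD, correlation 0.3 with fat | −0.47 | −0.05 |

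In the first row the false ACME is −0.48 at *a* = 1 and −1.44 at *a* = 3. It is within 0.02 pp of zero if *a* = 0 or if baseline fat is unrelated to risk. Adding HbA1c without baseline fat leaves −0.96 in the first row.

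**At 62 participants** (first-row assumptions, converged runs):

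| 12-month rate | Expected events (62 × rate) | Mean false ACME | 95% interval excludes 0 |
|---|---|---|---|
| 5% | 3.1 | −0.6 pp | 1.3% |
| 10% | 6.2 | −1.0 pp | 2.2% |
| 20% | 12.4 | −1.9 pp | 4.5% |

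At the 5% rate about a third of runs had no events or did not converge. With 1,000 participants, the same model was falsely significant in 73%, 96% and 99.5% of runs, against 3.0–5.5% after adjustment.

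**Cost of adjustment**, under the first set of assumptions. The variance inflation is 1/(1 − 49/53) = 53/4 = 13.25, so the slope's standard error grows by √13.25 = 3.6. In a simulation of 62 people at a 10% rate (about 7 events), the SD of the slope rose from 0.066 to 0.245 when baseline fat was added, and the root mean squared error from 0.095 to 0.245. At 5% and 20% rates the latter rose from 0.110 to 0.407 and from 0.079 to 0.171.

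**The case against.** The strongest reply is that the remedy costs more accuracy than it gains here. By root mean squared error the adjusted slope is roughly two to four times worse at 62 participants. That stands as a description of precision. It does not rescue the unadjusted estimate as a causal quantity; it shows that so few events cannot support a firm mediation claim either way.

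The SAP says what the outcome model includes and does not say that nothing else may enter. It also does not state that the level of fat is used; if change enters, the 92% argument does not apply as given. Both points are fair. A reader might infer that the SAP rules out baseline covariates, and the text does not go that far. But a plan that names no adjustment set and no form for the mediator leaves both to be chosen once data are in hand.

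The mention of a sensitivity analysis is also a partial answer. It is worded as a possibility, and such an analysis probes unmeasured confounding; it does not replace adjustment for variables already measured.

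Finally, Protocol section 1b calls this a pilot and feasibility trial, defers onset to a later trial, and lists neither onset nor mediation among its aims. That limits the weight of the point. It also means that the model may be carried into the larger trial, where the bias would become a false finding.

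**Conclusion.** The concern holds in conditional form. With the terms listed, the ACME and proportion mediated are biased away from zero if three things are true: the level of body fat enters, the programme lowers body fat, and baseline fat or a correlate such as HbA1c predicts onset. The second is what the programme is meant to achieve, and Protocol section 3a makes the third plausible by tying excess weight to T2D progression, but the documents give no figure for either. All sizes above therefore rest on assumption. The direction (given that higher baseline fat or HbA1c raises risk) and the disappearance of the bias once baseline fat is added do not depend on the exact values.

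Two stronger readings should be resisted. A reader might infer that the model will report mediation whatever the truth; it will not if the programme leaves fat unchanged, or if neither baseline fat nor its correlates predict onset. A reader might also infer that this trial is likely to declare a false mediated effect; at 62 participants the interval excluded zero in at most 4.5% of runs. The problem at this size is a biased and very imprecise point estimate.

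**What to change.** Amend the mediation paragraph of the SAP to:

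- include baseline percent body fat (essential) and baseline HbA1c in the outcome model, and condition the mediator model on both; using change in fat with baseline fat retained as a covariate is equivalent;
- take one mediator value per participant, from the post-test visit, and count only onsets detected after that visit;
- commit to the sequential-ignorability sensitivity analysis;
- report the ACME and proportion mediated as exploratory, with intervals.

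No new data are needed. The change is more than a word or two: the Aim 1 body-fat model has repeated values as its response, so a post-test mediator model conditional on baseline would take its place in this analysis. The main cost is the loss of precision from the collinearity of baseline and follow-up fat. With few events the interval will be very wide and the model may fail to converge, which the SAP should acknowledge in advance.
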